## 1 SYNOPSIS

**Title of Study:** A Multicenter, Double-blind, Randomized, Controlled Study of the Safety and Effectiveness of PN40082 for Lip Augmentation

**Name of Sponsor:** Prolenium Medical Technologies Inc.

**Name of Finished Product:** PN40082

**Device Composition:** Hyaluronic acid gel with lidocaine (0.3% w/w)

**Objectives:** To compare the safety and efficacy profile of PN40082 versus Restylane Silk Injectable Gel with 0.3% lidocaine (Restylane Silk) for lip augmentation.

**Study Design:** This is a double-blind, randomized, controlled, multicenter clinical study of subjects seeking lip augmentation. Subjects meeting inclusion/exclusion criteria will be randomized 1:1 to treatment with either PN40082 or Restylane Silk. The Evaluating Investigator will be blinded to the treatment. Injections of the study device will be performed by an unblinded Treating Investigator.

At each visit, the blinded Evaluating Investigator evaluations and subject evaluations of the treated areas will be performed and recorded. Visits and telephone contacts will occur at:

Visit 1 / Week 0 (Day 1) – baseline and treatment

-Day 3 ( $\pm 2$  days) - Safety follow-up telephone call

-Day 14 ( $\pm 2$  days) – Safety follow-up telephone call

Visit 2 / Day 28 ( $\pm 2$  days) / Month 1 – interim visit (touch-up if necessary)

-Day 33 ( $\pm 2$  days) – Safety follow-up telephone call (for subjects with touch-up treatment)

-Day 44 ( $\pm 2$  days) – Safety follow-up telephone call (for subjects with touch-up treatment)

Visit 3 / Day 56 ( $\pm 4$  days) / Month 2 – interim visit

Visit 4 / Day 84 ( $\pm 4$  days) / Month 3 – interim visit

-Day 112 ( $\pm 4$  days) / Month 4 – Safety follow-up telephone call

-Day 140 ( $\pm 4$  days) / Month 5 – Safety follow-up telephone call

Visit 5 / Day 168 ( $\pm 7$  days) / Month 6 – End of Study (EOS) Visit. All subjects will undergo the consent procedure for the open-label retreatment protocol.

Evaluations include:

Lip Fullness Grading Scale (LFGS) (Overall lip fullness considering both lips together, fullness of the upper lip and fullness of the lower lip)

Perioral lines at rest severity scale (POL) (Overall perioral lines at rest severity considering both lips together, perioral lines at rest severity of the upper lip and perioral lines at rest severity of the lower lip)

Patient Global Aesthetic Improvement (pGAI)

Investigator Global Aesthetic Improvement (iGAI)

Safety will be assessed by monitoring adverse events (AEs) at all study visits

Other Safety Evaluations include:

- Lip Function
- Lip Sensation
- Lip Texture
- Lip Firmness
- Lip Symmetry
- Lip Movement/Function

Other evaluations include:

- Investigator Ease of Use Assessment
- Swelling Assessment
- Subject Satisfaction with Lips Assessment

**Number of Study Centers:** Approximately 7 sites in the United States

**Duration of Participation:** Subjects will participate in the study for approximately 6 months from the time they sign the informed consent form (ICF) through the EOS visit.

**Duration of Study:** The study will require approximately 20 months from the first subject signing the ICF to the Month 6 EOS visit for the last subject

**Number of Subjects:** Approximately 158 subjects will be randomized

**Inclusion Criteria:**

1. Men or non-pregnant or non-breastfeeding women over 21 years of age
2. If female and of childbearing potential, a negative urine pregnancy test at Baseline (Day 1) and the subject agrees to use adequate contraception during the study period
3. Has an overall score of very thin, or thin on the LFGS, as agreed upon by the Treating and Evaluating Investigators, and desires at least a 1-point improvement in overall LFGS score; OR  
Has a Fitzpatrick skin phototype IV, V or VI and has an LFGS score of thick or full, as agreed upon by the Treating and Evaluating Investigators, and desires treatment to the vermilion body of 1 or both lips
4. Willing to give written informed consent

**Exclusion Criteria:**

1. Women who are pregnant, lactating, or planning a pregnancy
2. History of allergy, anaphylaxis or hypersensitivity to injectable hyaluronic acid products, local anesthetics of the amide type such as lidocaine, or to latex, or is planning to undergo desensitization therapy during the study

3. Has lip tattoos, piercings, facial hair, or scars that would interfere with visualization of the lips and perioral area for the effectiveness assessments
4. Has abnormal lip function, with inability to effectively sip water through a straw
5. Has abnormal lip sensation, with inability to feel a 0.4G monofilament or a cotton wisp at any site on the lip
6. Has moderate or severe abnormal lip asymmetry
7. Has any mass formation on the lip
8. Has dentures or any device covering all or part of the upper palate, and/or severe malocclusion or dentofacial or maxillofacial deformities as judged by the Treating Investigator. Subjects planning to undergo extensive dental procedures such as dental implants, multiple tooth extractions, or oral surgery should not participate. Minor dental procedures such as teeth cleaning and repair of caries are not exclusionary
9. Has undergone facial plastic surgery or received permanent facial implants (e.g., polymethylmethacrylate, silicone, polytetrafluoroethylene, polyacrylamide, lifting threads) anywhere in the face or neck, or is planning to be implanted with any of these products during the study
10. Has undergone semi-permanent dermal filler treatment (e.g., calcium hydroxylapatite, poly-L-lactic acid) in the lower face (below the orbital rim) within 12 months before enrollment or is planning to undergo such treatment during the study
11. Has undergone facial tissue augmentation with fat injections, botulinum toxin injections in the lower face (below the orbital rim), mesotherapy, or cosmetic procedures in the face or neck (e.g., face-lift, laser, photo-modulation, intense pulsed light, radio frequency, dermabrasion, moderate or greater depth chemical peel, microneedling, or other ablative procedures) within 9 months before enrollment or is planning to undergo any of these procedures during the study
12. Has used ANY lip filling agents within 12 months of study enrollment (hyaluronic acid products, collagen-based products, etc.)
13. Has used any lip plumping products or devices within 10 days before enrollment or is planning to use such products during the study
14. Has begun using any over-the-counter (OTC) or prescription oral or topical anti-wrinkle products for the lips or around the mouth within 90 days before enrollment or is planning to begin using such products during the study (Subjects who have been on a stable regimen of such products for at least 90 days are eligible for the study and must continue their regimen throughout the study.)
15. Is on an ongoing regimen of anticoagulation therapy (e.g., warfarin), thrombolytics, or inhibitors of platelet aggregation or nonsteroidal anti-inflammatory drugs (NSAIDs, e.g., aspirin, ibuprofen) or other substances known to increase coagulation time (e.g., herbal supplements with garlic or ginkgo) within 10 days of undergoing study device injections. Subjects who will withhold such therapy for 10 days before AND after any injection session may participate

16. Has a history or presence of bleeding disorders
17. Has used systemic corticosteroids or immunosuppressive medications within 30 days prior to treatment
18. Is on a concurrent regimen of lidocaine or structurally related local anesthetics (e.g., bupivacaine)
19. Has an active inflammation (skin eruptions such as cysts, pimples, rashes, or hives), infection, cancerous or precancerous lesion, or unhealed wound on the face
20. Has a history of known susceptibility to keloid formation or hypertrophic scars
21. Has porphyria
22. Has active herpes labialis lesions at the time of injections. Subjects with a history of herpes labialis who have had four (4) or more outbreaks in the 12 months prior to enrollment are also excluded even in the absence of lesions at the baseline visit
23. Has impaired cardiac conduction, severely impaired hepatic function, or severe renal dysfunction that, in the opinion of the investigator, would place them at risk of associated complications from these illnesses during the course of the study
24. Has any uncontrolled disease, i.e., a condition that has not been appropriately diagnosed, evaluated, and received medically appropriate treatment or care
25. Has severe cardiovascular disease; examples include but are not limited to New York Heart Association heart failure classification III or IV, unstable angina, and internal pacemakers. Potential subjects with other significant cardiovascular diseases should be discussed with the Medical Monitor before enrolling

### Study Devices

**Test device:** PN40082: a clear, colorless gel in 1.0 mL pre-filled syringes with 25 mg/mL of stabilized hyaluronic acid and lidocaine 0.3% w/w

**Comparator device:** Restylane Silk: a clear, colorless gel in 1.0 mL pre-filled syringes formulated to a concentration of 20 mg/mL of stabilized hyaluronic acid and lidocaine 0.3% w/w

### Statistical Methods

#### Sample Size Determination:

A total of 158 subjects will be randomized.

#### Analysis Populations:

Intent-to-treat (ITT/safety) population: All randomized subjects who received study device

Modified intent-to-treat (mITT): All randomized subjects who met the inclusion/exclusion criteria, were randomized, and received study device

Per-protocol (PP): All randomized subjects who met all inclusion/exclusion criteria; received study device, completed Visit 5 within the specified window; had LFGS score by the Blinded Evaluating Investigator at Visit 3/Month 2 within the specified visit window, and had no significant protocol violations that would affect the treatment evaluation

Efficacy analyses will be performed on the mITT and PP populations, with PP as the primary population and mITT supportive.

Safety analyses will be performed on the ITT population.

**Efficacy Analysis:**

The primary efficacy endpoint is change from baseline to Month 2 in overall lip fullness based on the Blinded Evaluating Investigator assessment using the LFGS. If the lower limit of the 95% confidence interval (CI) for (PN40082 minus Restylane Silk) with respect to the primary endpoint is above a pre-specified NI limit -0.50, PN40082 will be claimed non-inferior to the Restylane Silk.

Secondary analysis include

- percent of subjects with treatment success (responder: overall LFGS based on the Blinded Evaluating Investigator Assessment) at Visit 3/Month 2 where responder is defined as a subject with at least a 1-grade increase from baseline on the LFGS post augmentation,
- percent of responders overall on the POL severity scale at Visit 4/Month 3 (defined as a subject demonstrating  $\geq 1$ -point improvement, i.e., decrease in severity, from baseline),
- change from baseline to Visit 4/Month 3 in overall LFGS based on the Blinded Evaluating Investigator Assessment,
- change from baseline to Visit 5/Month 6 in overall LFGS based on the Blinded Evaluating Investigator Assessment.

Other efficacy analysis include

- pGAI, iGAI, and Swelling Assessment at each scheduled visit,
- percent of subjects with treatment success (responder: upper lips, lower lips LFGS) at Visit 3/Month 2 where responder is defined as a subject with at least a 1-grade increase from baseline on the LFGS post augmentation,
- percent of responders (upper lips, lower lips) on the POL severity scale at Visit 4/Month 3 (defined as a subject demonstrating  $\geq 1$ -point improvement, i.e., decrease in severity, from baseline),
- satisfaction with lips VAS at each scheduled visit,
- change from baseline to Visit 4/Month 3 and Visit 5/Month 6 in upper lips, lower lips LFGS.

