### **7.6.16 Swelling Assessment**

Swelling will be assessed by the Blinded Evaluating Investigator at Visits 2, 3, 4, and 5 using the 5-point scale with the categories that follow. The blinded Evaluating Investigator should examine both upper and lower lip simultaneously and recall the degree of augmentation originally provided for comparison. The subject should not be specifically questioned regarding swelling but if the subject spontaneously reports it, such information can be used to assist in selection of a grade for swelling.

0: None – No swelling noticeable. Lips appear the same as when originally augmented. Any lip enlargement is due to the implanted product only.

1: Minimal – Slight enlargement of either lip beyond the originally provided augmentation. May or may not be noticeable to the subject but is noticeable to the investigator.

2: Mild – Some enlargement of either lip beyond the original augmentation that is easily noticeable to the subject, but the lips do not appear abnormally large.

3: Moderate – Significant enlargement of either lip beyond the original augmentation. Either lip appears abnormally large.

4: Severe – Any degree of swelling that substantially interferes with lip function such as changes in speech or difficulty eating or drinking.

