**Figure 1. Visual Analog Scale for Subject Satisfaction**

### 7.6.24 Subject Diary Card

A diary card will be dispensed to each enrolled subject at Visit 1/Day 1. The subject will be instructed to complete the diary cards to record any AEs experienced during the 2 weeks after receiving the initial treatment and the touch up treatment. The diary cards will be collected at Visit 2/Month 1 and Visit 3/Month 2 if touch up treatment was given. A new diary card will be dispensed at Visit 2/Month 1 if touch up treatment is given.

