### **7.9.5 Monitoring Adverse Events**

Each subject will be monitored for the occurrence of AEs, including SAEs, immediately after treatment initiation. Each subject will be followed for safety monitoring until discharged from this study. Follow-up procedures related to pregnancy or AEs or SAEs may continue beyond the end of the study.

Subjects will be questioned and/or examined by the investigator or a qualified designee for occurrence of AEs throughout the study. The presence or absence of specific AEs should not be elicited from subjects. In addition, subjects will be instructed to record AEs on the subject diary card during the 2 weeks after treatment. Subjects having AEs will be monitored with relevant clinical assessments and laboratory tests, as determined by the investigator.

AEs, actions taken as a result of AEs, and follow-up results must be recorded on the CRF, as well as in the subject's source documentation.

For all AEs that require the subject to be withdrawn from the study and SAEs, relevant clinical assessments will be repeated as clinically appropriate until final resolution or stabilization of the event(s).

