**WARNINGS**

- Defer use of *Restylane Silk* at specific sites in which an active inflammatory process (skin eruptions such as cysts, pimples, rashes, or hives) or infection is present until the process has been controlled.
- Injection site reactions (e.g., lip swelling, lip pain, and contusion) to *Restylane Silk* have been observed as consisting mainly of short-term minor or moderate inflammatory symptoms starting shortly after treatment, with an average of less than 18 days duration in the lips. In some cases delayed onset of these events has been observed with a range of 21 to 142 days after treatment. Most events with delayed onset resolved within 18 days. Injection site swelling appears to occur more frequently with the linear antegrade method of injection. Rare post-market *Restylane* reports of immediate post-injection reactions included extreme swelling of lips, the whole face and symptoms of hypersensitivity such as anaphylactic shock.
- Introduction of product into the vasculature may lead to embolization, occlusion of the vessels, ischemia, or infarction. Take extra care when injecting soft tissue fillers, for example inject the product slowly and apply the least amount of pressure necessary. Rare but serious adverse events associated with the *intravascular* injection of soft tissue fillers in the face have been reported and include temporary or permanent vision impairment, blindness, cerebral ischemia or cerebral hemorrhage, leading to stroke, skin necrosis, and damage to underlying facial structures. Immediately stop the injection if a patient exhibits any of the following symptoms, including changes in vision, signs of a stroke, blanching of the skin, or unusual pain during or shortly after the procedure. Patients should receive prompt medical attention and possibly

evaluation by an appropriate health care practitioner specialist should an intravascular injection occur.

- *Restylane Silk* must not be implanted into blood vessels. Localized superficial necrosis and scarring may occur after injection in or near vessels, such as in the lips, nose, or glabellar area. It is thought to result from the injury, obstruction, or compromise of blood vessels.
- Delayed onset inflammatory papules have been reported following the use of dermal fillers. Inflammatory papules that may occur rarely should be considered and treated as a soft tissue infection.

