- necessitates medical or surgical intervention to preclude permanent impairment of a body function or permanent damage to a body structure.

Subjects were asked to grade symptoms of bruising, redness, swelling, pain, tenderness and itching. Subject's scores for the severity of these events are presented in Table 2 and durations are provided in Table 3. The majority of events (>85%) were mild in intensity and resolved in 2 – 7 days. Eight patients reported diary symptoms of "Affects Daily Activities" and "Disabling" that lasted longer than 7 days. These events were: Swelling (n=6), pain (n=2), tenderness (n=3), bruising (n=3), itching (n=2), and redness (n=1).

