**Table 2: MA-1700-04 Duration of Symptoms from Patient Diary**

No Treatment at Baseline (N=44)					
	Number of Days				
	Any N (%)	1 n (%)	2 - 7 n (%)	8 - 13 n (%)	14 n (%)
Upper and Lower Lip Combined					
Bruising	0	0	0	0	0
Redness	0	0	0	0	0
Swelling	1 (2%)	0	1 (100%)	0	0
Pain (includes Burning)	1 (2%)	1 (100%)	0	0	0
Tenderness	1 (2%)	1 (100%)	0	0	0
Itching	0	0	0	0	0
First Treatment with Restylane Silk (N=218)					
	Number of Days				
	Any N (%)	1 n (%)	2 - 7 n (%)	8 - 13 n (%)	14 n (%)
Upper and Lower Lip Combined					
Bruising	176 (81%)	10 (6%)	130 (74%)	34 (19%)	2 (1%)
Redness	152 (70%)	40 (20%)	97 (64%)	15 (10%)	0
Swelling	213 (98%)	9 (4%)	149 (70%)	40 (19%)	15 (7%)
Pain (includes Burning)	167 (77%)	43 (20%)	110 (66%)	13 (8%)	1 (<1%)
Tenderness	199 (91%)	17 (9%)	132 (68%)	41 (21%)	9 (5%)
Itching	64 (29%)	21 (33%)	34 (53%)	7 (11%)	2 (3%)
Second Treatment with Restylane Silk (N=133)					
	Number of Days				
	Any N (%)	1 n (%)	2 - 7 n (%)	8 - 13 n (%)	14 n (%)
Upper and Lower Lip Combined					
Bruising	89 (67%)	6 (7%)	65 (73%)	17 (19%)	1 (1%)
Redness	89 (67%)	18 (20%)	64 (72%)	7 (8%)	0
Swelling	124 (93%)	2 (2%)	96 (77%)	20 (16%)	6 (5%)
Pain (includes Burning)	100 (75%)	26 (28%)	70 (70%)	4 (4%)	0
Tenderness	118 (89%)	8 (7%)	88 (75%)	19 (16%)	3 (3%)
Itching	37 (28%)	8 (22%)	21 (57%)	8 (22%)	0

The treatment-emergent adverse events (TEAEs) reported during the study are presented in Table 1. The number of events and subjects reporting TEAEs decreased between the first and second treatments. Seventy-eight percent (169/281) of subjects receiving their first treatment reported a total of 632 TEAEs while 63% (84/133) of subjects that received a second treatment reported a total of 196 TEAEs. Furthermore, an overwhelming majority of these TEAEs were mild in intensity (540/632; 85%, and 178/196; 91%; first and second treatment respectively), and were transient in nature, resolving in a mean of 17.4 days (median 10 days).

The most common TEAEs occurring after initial treatment with *Restylane Silk* were lip swelling (43%), contusion (44%), and lip pain (10%). There was no increased risk with additional treatment with *Restylane Silk*. After the second treatment, the reported incidence decreased to 35%, 31%, and 7%, respectively.

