3.1 Study Design

For the purpose of exploring the above objectives, the study will be conducted as a multicenter, double-blind, randomized, controlled study in subjects seeking lip augmentation. Subjects will be randomized 1:1 to treatment with either PN40082 or Restylane Silk. The treating investigator will be performing assessments at baseline to confirm inclusion/exclusion criteria entry. The Evaluating Investigator and subject will be blinded to the treatment. Injections of the study device will be performed by an unblinded Treating Investigator. At each visit, the blinded Evaluating Investigator and subject evaluations of the treated areas will be performed and recorded. Visits will occur at:

- Visit 1 / Week 0 (Day 1) – baseline and treatment
- Visit 2 / Day 28 (± 2 days) / Month 1 – interim visit (touch-up if necessary)
- Visit 3 / Day 56 (± 4 days) / Month 2 – interim visit
- Visit 4 / Day 84 (± 4 days) / Month 3 – interim visit
- Visit 5 / Day 168 (± 7 days) / Month 6 – End of Study (EOS) Visit. All subjects will undergo the consent procedure for the open-label retreatment protocol.

Telephone contacts for safety follow-up will occur at:

- Day 3 (± 2 days) - Safety follow-up telephone call
- Day 14 (± 2 days) – Safety follow-up telephone call
- Day 33 (± 2 days) – Safety follow-up telephone call (for subjects with touch-up treatment)
- Day 44 (± 2 days) – Safety follow-up telephone call (for subjects with touch-up treatment)
- Day 112 (± 4 days) / Month 4 – Safety follow-up telephone call
- Day 140 (± 4 days) / Month 5 – Safety follow-up telephone call

Evaluations include:

- Lip Fullness Grading Scale (LFGS) (Overall lip fullness considering both lips together, fullness of the upper lip and fullness of the lower lip)

- Perioral lines at rest severity scale (POL) (Overall perioral lines at rest severity considering both lips together, perioral lines at rest severity of the upper lip and perioral lines at rest severity of the lower lip)
- Patient Global Aesthetic Improvement (pGAI)
- Investigator Global Aesthetic Improvement (iGAI)
- Swelling Assessment
- Subject Satisfaction with Lips Assessment (using VAS)

Safety will be assessed by monitoring adverse events (AEs) and concomitant medications at all study visits. Other Safety evaluations include lip function, lip sensation, lip texture, lip firmness, lip symmetry and lip movement/function. Other evaluations include Investigator Ease of Use Assessment.

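### The graded Swelling Assessment has no scheduled use in the acute period, so acute swelling is compared only through AE reports that, as far as the documents show, are unprompted

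*Protocol*

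**What the plan says.** The protocol synopsis (Efficacy Analysis) places "pGAI, iGAI, and Swelling Assessment at each scheduled visit" under other efficacy analysis. Protocol 7.6.16: "Swelling will be assessed by the Blinded Evaluating Investigator at Visits 2, 3, 4, and 5 using the 5-point scale". The Schedule of Activities agrees, with no swelling grade at Visit 1 and none between Visit 1 and Visit 2. An unscheduled visit (7.7.8) may include one if needed. SAP 5.5.3 treats the scale as a descriptive other efficacy variable.

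Three provisions cover the acute period:

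- The diary (7.6.24) is for subjects to "record any AEs experienced during the 2 weeks after receiving the initial treatment and the touch up treatment". No named symptoms or intensity scale are described.
- Calls on Days 3 and 14, and on Days 33 and 44 after a touch-up, assess AEs.
- Section 7.9.5 adds: "The presence or absence of specific AEs should not be elicited from subjects".

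Under 7.9.8, returned diaries are reviewed by the Treating Investigator and/or unblinded staff. Events that outlast the diary become AEs only at the investigator's discretion.

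The Restylane Silk Instructions for Use, attached to the protocol, show how the comparator was studied. In the pivotal study (MA-1700-04), "Subjects were asked to grade symptoms of bruising, redness, swelling, pain, tenderness and itching". The cannula study (43USC1505) also used a 14-day diary of the same six symptoms with intensity. The label's Warnings describe injection-site reactions "with an average of less than 18 days duration in the lips", and also delayed onset 21 to 142 days after treatment.

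**The concern.** The study objective includes comparing the safety of the two devices. A by-visit table headed Swelling Assessment invites the reader to take it as the comparison of swelling. If nearly all acute swelling has gone before the first grade, that table will show mostly grade 0 in both arms, even if the devices differ in how much or how long lips swell in the first two weeks. Such a difference would then have to be found in AE reports that subjects volunteer. Nor could the results be set beside the comparator's own graded diary data, because the capture method differs.

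**Working it through.** **Inputs.** From the Restylane Silk Instructions for Use (MA-1700-04):

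- Lip swelling TEAE after first treatment: 94 of 218 subjects; duration mean 7.3 (SD 4.1), median 6.0, range 2 to 21 days.
- After second treatment: 46 of 133; mean 7.4 (SD 8.1), median 5.0, range 1 to 38 days.
- Diary swelling after first treatment: 213 of 218, of whom 9 had it for 1 day and 149 for 2 to 7 days.
- Onset more than 3 weeks after injection: 35 lip events, 26 of them lip swelling.

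From protocol 8.5: 79 subjects randomized per arm.

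**Stated figures reproduced.** 94/218 = 43.1% (stated 43%). 213/218 = 97.7% (stated 98%). Diary swelling of 7 days or less: (9 + 149)/213 = 74%.

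**Timing.** Visit 2 falls on Day 26 to 30, with injection on Day 1.

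- After first injection: 26 − 1 = 25 to 30 − 1 = 29 days. Even the earliest Visit 2 is later than the longest first-treatment swelling (21 days), provided that swelling begins within 25 − 21 = 4 days of injection.
- After a touch-up at Visit 2, the next grade is Visit 3 (Day 52 to 60): 52 − 30 = 22 to 60 − 26 = 34 days. The second-treatment maximum of 38 days can reach this.

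**First-treatment swelling left at Visit 2.**

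- None of 94 durations reached 25 days. Exact 97.5% upper bound: 1 − 0.025^(1/94) = 3.8%.
- As a cross-check, assume lognormal durations. Fitted to median and mean, σ = √(2 ln(7.3/6.0)) = 0.626 and P(T > 25) = 1 − Φ(ln(25/6)/0.626) = 1.1%. Fitted to mean and SD, P(T > 27) = 0.3%.
- Per arm of 79: 79 × 94/218 = 34 subjects with a swelling TEAE, and at most 34 × 0.038 = 1.3 still swollen.

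**After touch-up.** For the second-treatment figures, σ = √(2 ln(7.4/5.0)) = 0.885, giving P(T > 28) = 2.6% and P(T > 22) = 4.7% of swelling events.

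**What the Visit 2 grade could detect.** Upper-bound prevalence is 0.431 × 0.0385 = 1.7%. Two-sided 5% test, 79 per arm, power = Φ[(|d| − 1.96·SE₀)/SE₁], with SE₀ pooled and SE₁ unpooled:

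| Comparison | Power |
|---|---|
| Day 28, 1.5-fold | 6% |
| Day 28, 2-fold | 10% |
| Day 28, 3-fold | 21% |
| Acute TEAE, 43% v 65% (about 1.5-fold) | 79% |

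The normal approximation is rough at such low rates, but the contrast is not in doubt: the information lies in the acute window.

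**What the scale can still see.** If the 26 late lip-swelling events are spread evenly over Days 21 to 142 (121 days) and last 7.3 to 18 days, prevalence on a given day is 26 × 7.3/(121 × 218) = 0.7% to 26 × 18/(121 × 218) = 1.8%. That is 0.6 to 1.4 subjects per arm of 79, which is few but not none.

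**What the SAP tabulates for acute events.** Tables 14.3.2.1 to 14.3.2.9 cover reporter, severity, number of injections and duration (under 7, 7 to 30, over 30 days). Their titles refer to vascular injections and visual events. However, a summary row in several shells refers to injection-site or visual TEAEs, and the example in Listing 16.2.7.1.1 is a diary-reported injection site swelling. Section 5.6.1 does not define the group. The complementary set (14.3.3.1 to 14.3.3.4) has no duration table.

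**The case against.** The strongest reply is that acute swelling is already compared. AEs carry severity, onset and resolution; 7.9.3.1 names swelling as an expected event; and the SAP shells appear to tabulate injection-site TEAEs by arm, severity, duration and before or after touch-up. This largely stands. A reader might infer that no acute comparison is planned, and the documents do not support that. What is left is how the reports are prompted.

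Second, the diary card is not in the documents, so it may already list symptoms, and the non-elicitation sentence may be aimed at questioning by staff rather than at the diary. Both are possible. The protocol should then say so, because its text describes only an open record of AEs.

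Third, subjects are blinded, so unprompted reporting should lose sensitivity similarly in both arms. No bias between arms is shown; the loss is in completeness and precision.

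Four stronger readings should be set aside:

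- That the scale cannot compare swelling at all. It can register late or delayed-onset swelling, and 26 of 35 late-onset lip events in the comparator study were swelling.
- That 21 days is the longest duration. That is first treatment only; after second treatment it was 38.
- That swelling is the commonest harm of both devices. It leads in diary data and in event counts (186 v 145), but by subjects with a TEAE contusion is slightly ahead (44% v 43%). The documents give no rate for PN40082.
- That 98% in the comparator diary against 43% as TEAEs, or 100% against 13.3% in the cannula study, measures what this trial would miss. Here diary entries can feed the AE listing. In the cannula study TEAEs were counted apart from diary events, and cannulas are prohibited in this trial.

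**Conclusion.** The Swelling Assessment has no scheduled grade before 25 to 29 days after injection and is close to uninformative about acute swelling. On comparator data at most 3.8% of first-treatment swelling would remain at Visit 2, about 1 subject per arm. It remains a usable check on late or persistent swelling. The comparison of acute swelling therefore rests on diary and telephone AE reports, which are unprompted as far as the documents show.

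This assumes that comparator durations carry over to PN40082, that acute swelling starts within about 4 days of injection, and that the diary card has no named symptoms beyond what 7.6.24 describes. The primary efficacy conclusion is not affected. This is a worthwhile, inexpensive improvement to the safety comparison rather than an error that invalidates it.

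**What to change.** 1. In 7.6.24, have the existing 14-day diary card list swelling, bruising, redness, pain, tenderness and itching, each with a daily intensity tick. If the card already does this, state it.
2. In 7.9.5, exempt the diary from the sentence against eliciting specific AEs.
3. In the SAP, add tables of maximum intensity and number of days by arm in the As-Treated population, after the first injection and after the touch-up. Keep them separate from the unsolicited TEAE tables so that prompted and volunteered events are not mixed.
4. Label the visit-based Swelling Assessment, in the text and in Table 14.2.3.3, as late or persistent swelling.

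Cost: a reprinted diary card, one sentence in each of two protocol sections, and two SAP tables. No extra visit or staff is needed. The downside is that prompting will raise recorded symptom counts in both arms and gives subjects a small daily task.
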